Baseline Visit (Visit 3): Female subjects will be instructed to come into the clinic within three days of the start of their Luteal Phase for their baseline visit and to start medication (PRO or PBO). Female subjects will self-report menstrual cycle length at their screening visit and staff will determine when their Luteal Phase will most likely begin. Male subjects will be instructed to come into the clinic according to their assigned delay (per randomization list generated by the Statistical Analysis Core). This visit will occur seven days prior to quit date. At this visit, subjects will be randomized to PRO or PBO within strata defined by sex. The Statistical Analysis Core (SAC) will generate the randomization tables (one for each sex, 1:1 allocation using randomly permuted blocks of size 2 and 4), and the Clinical Trials Research Pharmacy will use it to determine randomization assignment. Randomization assignment will be stored in a secure file in a secure location at the Clinical Trials Research Pharmacy, to be shared only with the SAC. All other project staff including PI and study coordinator, as well as the participant, will remain blinded to the randomization assignment. At the baseline visit subjects will provide a blood sample (for hormone assessment), urine sample for THC, breath sample (to confirm smoking status via carbon monoxide breathalyzer), have their vital signs (blood pressure, heart rate, weight) measured, be informed of their quit date, and receive brief behavioral counseling to prepare for their quit date. At the end of this visit subjects will be compensated for their time, given study medication along with instructions for taking the medication (beginning at 8PM that day), as well as a clinic visit schedule for the remaining clinic visits. This visit will take approximately one hour to complete.

Marijuana Change Date Assignment: Change date (Week 0) will be set for 7 days following the Baseline Visit. Since this entails a delay of variable duration from Screening Visit 2 to Baseline Visit (thus impacting timing of medication initiation) across female subjects, each male subject will be matched to a female subject for a similar delay so that, across the male and female groups, study procedures will follow a similar chronology.

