- Weeks 0-5 (Visits 4-9):** The Week 0 clinic visit will occur on the assigned “Marijuana Change Date”. Subjects will attend clinic visits on a weekly basis thereafter for 5 weeks. At weeks 0, 2, 4, and 5, blood samples will be collected and stored for the analysis of hormones. Urine samples will be collected at each

clinic visit for the visual inspection of riboflavin (assessing medication compliance), biochemical confirmation of THC, and for a pregnancy test (females only). Urine will be saved and stored on Weeks 0, 2, 4, and 5 for cotinine analysis.

Subjects will also complete several forms and questionnaires (described below). Subjects will return the medication bottle and unused medication, be given a new one-week supply and adverse events will be assessed. At Week 4, subjects will complete impulsivity tasks and study medication will be discontinued. Finally, subjects will receive brief, behavioral counseling at each clinic visit. At the end of each visit subjects will be paid for their time. These visits will take approximately 30-45 minutes to complete.

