Therefore, subjects will receive approximately \$340 (\$25 Screening Visits x 2 visits + \$20 follow-up visits x 7 visits + \$80 in bonus payments + an average of \$70 in BART payments).

Study Medication

Subjects will be stratified by sex and then randomly assigned to PRO or PBO, as described above. All medication (active and placebo) will be prepared by the University of Minnesota Clinical Trials Research Pharmacy, which is a specialized facility that prepares medication for clinical trials including our ongoing research. The research pharmacist ([name] Pharm D) will provide medications. There will be oversight and monitoring with regular audits by local regulatory boards including the IRB and DSMB. This study requires double-blind procedures, therefore progesterone will be over encapsulated and be identical to the placebo capsules. Medications will be discontinued at the Week 4 clinic visit. Adverse events will be assessed at each clinic visit.

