Progesterone: The progesterone will be given in the form of an active or placebo micronized natural progesterone (generic Prometrium). All subjects will take 200 mg twice daily (approximately 8am and 8pm) for five weeks starting seven days prior to the assigned change date. The dosage was selected to ensure that serum progesterone levels will be consistent with those observed in the natural Luteal phase of the menstrual cycle (6-14 ng/mL) since that phase has been shown to be favorable for smoking cessation ([name] et al 2008). We expect the following serum progesterone levels by group (Figure 5): (1) females + PRO 9-13 ng/mL; (2) males + PRO 6-7 ng/mL; (3) females + PBO, varies by menstrual phase from 1-14 ng/mL; and (4) males + PBO 0-1 ng/mL (Goletiani et al 2007; Reed et al 2010; Yen et al 1999). Delivery of exogenous progesterone has been successfully used in other studies and is generally well tolerated (Sofouglu et al 2001; Sofouglu, et al 2004; Goletiani et al 2007; Reed et al 2010). The most common adverse effect in males and females is sedation. Less common effects include breakthrough bleeding (females), nausea (females and males) and breast tenderness (females) (de Lignieres, 1999; Goletiani et al 2007). While it is possible that progestins may contribute to risk for thromboembolism, we will be using natural micronized progesterone instead of synthetic progestins. Natural micronized progesterone is not known to be associated with thromboembolic risk (PDR, 2002; Goletiani et al 2007), and consequently is a safer choice. Micronized progesterone is not a form of birth control. Therefore, all female subjects will be educated on the importance of using a double-barrier method to protect against pregnancy.

Study Measures

We will assess marijuana use using two methods (self-report, biochemical confirmation). *First*, at each clinic visit the TimeLine Follow-Back (TLFB) method will be completed. The TLFB is a validated retrospective data capture technique (Sobell et al 1996). *Second*, at each clinic visit we will measure urinary THC levels (see table 1 for all study measures and when they are collected).

Impulsivity Measures: Subjects will complete *three self-report measures* that have been computerized at each clinic visit beginning at Screening Visit 2. These measures will assess the characteristics of impulsivity, inhibition, planfulness, and cognitive impairments, key areas of focus in this grant.

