Randomization, assignment (PRO vs. placebo) will be known as of the Baseline Visit to the SAC and Clinical Trials Research Pharmacy, but not will be known to other staff or participants until after completion of all measurements. Participants will be informed on their randomization assignment in a letter mailed within six months of the study’s completion; this letter will also briefly summarize the study’s findings.

Measurement of serum progesterone will be measured by collecting a blood sample at Screening, Bassline and Weeks 0, 2, 4, and 5.. Blood (20cc) will be drawn then centrifuged. The serum stored at -20°C in sealed storage tubes to prevent evaporation. Approximately two mL of serum will be analyzed by the University of Minnesota Laboratories for progesterone sample. The remaining serum (approximately two to four mL) will be used for estradiol measurement (described below) and/or stored as back-up to be used in the event that problems occur during analyses.

Other Covariates: Information on potential covariates is collected at the clinic visits, including:

- **Cannabis Use Disorder ID test (CUDIT-R, Adamson et al 2010):** This item is 8 questions that screens for

problematic cannabis use. The domains captured in this questionnaire are consumption, abuse, dependence and psychological features. This screening test has been shown to have 91% sensitivity and 90% specificity. This item will be completed at Screening Visit 1.

- **Marijuana Craving Questionnaire** (MCQ-SF; Heishman et al 2008): This item includes 12 questions that assess 4 characteristics of craving, compulsivity, emotionality, expectancy and purposefulness. This item will be completed at Screening Visit 1. This item will be completed at each clinic visit thereafter.
- **Cannabis Withdrawal Scale** (CWS; Allsop et al 2011): This item measures the intensity of cannabis withdrawal symptoms and the distress or functional impairment caused by each symptom using a 10-point Likert scale. This item will be completed at Screening Visit 1. This item will be completed at each clinic visit thereafter.
- **Severity of Dependence Scale Cannabis** (SDS-C; Swift et al 2000): This 5 item questionnaire is sensitive to the severity of cannabis dependence. This item will be completed at Screening Visit 1.

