- **Serum Estradiol**: Blood samples will be collected at Screening, Baseline and Weeks 0, 2, 4, and 5 to allow for the measurement of serum estradiol. Following identical procedures described above for serum progesterone, approximately two mL of serum will be analyzed by University of Minnesota Laboratories.
- **Leisure Time Exercise Questionnaire** (LTEQ): This questionnaire has four-items to assess strenuous, moderate and mild exercise completed during leisure time and has high reliability ($r=0.83, 0.85$; Gordin & Shepard, 1985). This item will be completed at Screening Visit 2. This item will be completed at each clinic visit thereafter.
- **Life Event Occurrence Survey** (LEOS; McKee et al, 2005): This item will assess and account for the presence of current or recent significant life events. This measure includes 38 yes/no questions assessing various events that may have happened in the last six months including aspects of work, social life, family and finances. The measure includes instructions on how to rate the level of disruption the event caused in the subjects life from none to severe disruption. This measure will be administered at screening visit 1 and the final visit W5.
- **Caffeine Use**: Caffeine use will be collected via self-report at each clinic visit using the TimeLine FollowBack methods in which participants will report the total number of ounces of caffeinated beverages drank per day for each of the last 7 days.
- **Tobacco Use**: Tobacco use will be collected via self-report at each clinic visit using the TimeLine FollowBack methods in which participants will report the total number of cigarette smoked per day for each of the last 7 days.
- **Adverse Childhood Experience (ACE)**: Participants will complete this form at the SC2 visit.

Debriefing Questionnaire: At end of study participation or Week 4, whichever is later, participants will complete a questionnaire to indicate which study medication (active or placebo) they thought they were on.

Table 1. Study Measures at Each Time Point

| | SC1 | SC2 | BL | Week 0 | Week 1 | Week 2 | Week 3 | Week 4 | Week 5 |
|---|--------|-----|----|--------|--------|--------|--------|--------|--------|
| Intake Form: Demographics, baseline characteristics | INTAKE | | | | | | | | |
| Medical History: Assess inclusion/exclusion criteria | MH | | | | | | | | |
| Structured Clinical Interview for DSM Disorders | SCID | | | | | | | | |

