Medical histories for all subjects will be reviewed prior to entry into the study and all subjects will be under medical supervision while in the study. Urine and breath samples will be obtained and should not present risk to the subjects. Blood samples will be obtained by trained phlebotomists. A minimal amount of blood will be collected (20cc) per collection. Blood drawing may result in slight discomfort, bruising, or there may be some soreness at the puncture site. In some cases there may be dizziness or fainting.

Progesterone is generally well tolerated. The most common adverse effect is sedation. Other less common adverse effects include menstrual irregularity (spotting or breakthrough bleeding; females only) dizziness, cramps, nausea, fatigue, headache and breast tenderness (de Lignieres, 1999; Simon, 1995, Sofuglu, 2009). Other side effects attributed to synthetic progesterone including depression, fluid retention, pruritus, jaundice, rash and thrombotic disorders, are unlikely to occur. Recently there have been reports of increased risk of stroke, coronary artery disease, venous thromboembolism and breast cancer in postmenopausal females who have been on long-term hormone replacement treatment with estradiol and progestin (medroxyprogesterone) combination (Anonymous, 2002; Grady et al., 2002; Hulley et al., 2002; Nelson et al., 2002). While some of these adverse events develop after years of treatment, venous thromboembolism is seen within the first year of treatment (Anonymous, 2002). It is possible that progestins may contribute to thromboembolism seen during estradiol and progestin treatment and thromboembolism is listed in the PDR as one of the adverse events for

medroxyprogesterone treatment (PDR, 2002). In contrast to synthetic progestins, natural progesterone is not known to cause thromboembolism (PDR, 2002). However, as a safety measure for these serious adverse events, we will exclude subjects with history of thrombophlebitis, deep vein thrombosis, pulmonary embolus, clotting or bleeding disorders, heart disease, diabetes or history of stroke. Possible adverse events from Progesterone will be assessed weekly by the research nurse ([name], NP) in consultation with the study physician ([name], MD). If the side effects cannot be tolerated the medication dosage will be decreased to 200 mg once/day for those on the active medication.

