Although uncomfortable, marijuana withdrawal symptoms do not pose significant health risks. Subjects who participate in this study will be asked to quit or reduce their marijuana use on an assigned quit date. This may result in increased irritability, anxiety, tension, decreased appetite or sleeplessness.

Adverse Events: An adverse event is any unwanted experience or event occurring during the course of a clinical trial. At each visit, research assistants will collect pertinent information on any AE's and meet with the Nurse Practitioner (NP) at least once per week. The NP will decide if the AE was related to the study medication and give recommendations for follow-up. In cases where the NP is unavailable or if the AE needs immediate attention, it will be escalated to the PI immediately for acknowledgment and recommendations.

The study investigators will follow all AEs to the point of a satisfactory resolution. A study subject may be withdrawn from the study if the PI determines it is the best decision for protection of the safety of the subject. All AEs will be assessed to determine if they meet criteria for an SAE. AEs will be quantified separately by sex and treatment groups and compared across treatment groups with Fisher's exact test (for binary events) or with chi-square test (for counts of events or event rates). The event will be documented as to whether there is 1) no relationship between the study drug and the adverse event, 2) the adverse event is unlikely related to administration of the study drug, 3) the adverse event is possibly related to study drug administration, or 4) the adverse event is probably related to the administration of the study drug.

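### The dose reduction for intolerance applies, as written, only to the active arm, so blinded staff cannot use it as worded without risk of revealing assignment

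*Combined protocol and SAP*

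**What the plan says.** The only dose-reduction rule is in Trial Safety, under the potential risks for participants: "If the side effects cannot be tolerated the medication dosage will be decreased to 200 mg once/day for those on the active medication". In the same paragraph the research nurse, consulting the study physician, assesses possible adverse events each week. Protection against Risk identifies the study physician as the PI.

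The blinding provisions are unqualified. The Baseline Visit section confines the assignment to the research pharmacy and the Statistical Analysis Core, and adds: "All other project staff including PI and study coordinator, as well as the participant, will remain blinded to the randomization assignment". The paragraph on randomization under Independent Measures gives the duration: assignment is known to those two groups, "but not will be known to other staff or participants until after completion of all measurements".

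On the medication itself:

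- Study Medication, Progesterone: "All subjects will take 200 mg twice daily (approximately 8am and 8pm) for five weeks".
- Study Medication: "This study requires double-blind procedures, therefore progesterone will be over encapsulated and be identical to the placebo capsules".
- Weeks 0-5: "Subjects will return the medication bottle and unused medication, be given a new one-week supply and adverse events will be assessed".

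**The concern.** The decision to reduce rests with people who must not know the arm, yet the action is worded to differ by arm. Identical capsules hide what is in them; they do not hide how many a participant takes each day. If only progesterone participants move to one dose a day, a reduction points to progesterone, and the absence of one after reported intolerance points to placebo.

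Placebo participants may well report troublesome symptoms. Everyone is asked to quit or cut down, and the protocol expects this may bring irritability, anxiety, tension or sleeplessness.

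The outcomes at risk depend on the blind. The primary outcome is the change in marijuana use on the Timeline Follow-Back, a self-report, at week 4 relative to baseline. Participants receive counseling at every clinic visit. For adverse events, "The NP will decide if the AE was related to the study medication and give recommendations for follow-up", and events are then compared between arms. Knowledge of the arm could shift reporting, counseling, retention and relatedness judgments, and would do so selectively in people with side effects.

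**Working it through.** No figure in the plan can be reproduced here. The check is a comparison of provisions, followed by two small calculations.

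**Provisions side by side**

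| Question | What the plan provides | Section |
|---|---|---|
| Who judges tolerability? | Research nurse with the study physician (the PI) | Trial Safety; Protection against Risk |
| Do they know the arm? | No | Baseline Visit; Independent Measures |
| Who knows the arm? | Research pharmacy and Statistical Analysis Core | Baseline Visit |
| Does the action depend on arm? | Yes, as worded | Trial Safety |
| What happens to a placebo participant with intolerable effects? | Not stated | – |
| How is the change made blind? | Not stated | – |

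**Could the arm qualifier be only descriptive?** It might mean no more than that a milligram dose has meaning for active capsules alone. But the Progesterone section gives the 200 mg regimen to all subjects, placebo included, without a qualifier. Having used milligrams for both arms there, the protocol adds a restriction only in the reduction rule. The more natural reading is that the action is limited to the active arm.

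**Visible change under the literal reading**

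- Standard weekly supply, both arms: 2 doses/day × 7 days = 14 doses.
- Reduced weekly supply, progesterone only: 1 dose/day × 7 days = 7 doses.
- Placebo participant with the same complaint: 14 doses, unchanged.

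**Weight of one affected participant**

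Hypothesis 1a is modeled separately by sex. Study Design plans 20 completers per drug group, half of them female.

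- Sex-by-arm cell at target: 20 × 0.50 = 10, so one participant is 1/10 = 10% of a cell mean.
- If all 70 enrolled give an outcome: 35 per sex ÷ 2 = 17.5 per cell, so 1/17.5 = 5.7%.
- For an estimate pooled over sex: 1/20 = 5%, or 1/35 = 2.9% if all 70 contribute.

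These are weights that any participant carries in these analyses. The bias would be the weight, times the number of people unblinded, times the shift in reporting that unblinding causes. The documents give neither of the last two.

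**The case against.** The strongest reply is that an arm-limited reduction need not be visible. The code-holding pharmacy prepares all medication, capsules are identical, bottles are replaced weekly, and the blind is stated without exception. Read in that light, the sentence in the risk section falls under the general blinding rule, and the pharmacy would replace one of the two daily capsules with placebo. What is missing would then be an undocumented pharmacy step. This reading is possible and cannot be excluded. However, the plan does not state it, and it fits poorly with a rule expressed as once-daily dosing. It also leaves open what happens to placebo participants.

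Several limits on the size of the problem stand. Progesterone is described as generally well tolerated, so few people may be affected. Sedation is its most common effect, so some of those people may already suspect their arm. A changed or unchanged schedule is informative only to someone who knows the rule is arm-specific; staff working from the protocol could know this, but nothing shows that participants are told. The 6–10% cell weights do not measure bias.

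There are also partial safeguards. Urine THC is measured at each clinic visit, and at the end "participants will complete a questionnaire to indicate which study medication (active or placebo) they thought they were on". Both may help to detect a problem afterwards; neither prevents it. That this is an estimation pilot with no power calculation lowers the stakes, but its estimates are meant to justify a larger trial, so an intact blind still matters.

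**Conclusion.** The concern holds: the rule is wrong as written. It makes an action triggered by blinded staff depend on the arm, and if carried out literally it could reveal assignment during the measurement period. This rests on reading the arm qualifier as limiting who is reduced, which the unqualified regimen for all subjects supports, and on there being no separate pharmacy procedure that already masks the change.

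The number of participants affected and the resulting bias cannot be quantified from the documents. What can be stated is the visible contrast (14 to 7 weekly doses on progesterone, 14 unchanged on placebo) and the weight of each affected participant in a sex-specific cell (about 6% to 10%). Confidence is medium because the benign reading remains open. The correction should be made, since it costs almost nothing under either reading.

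**What to change.** Reword the sentence in Trial Safety without reference to arm. Blinded staff request a reduction for any participant whose side effects cannot be tolerated, and the pharmacy carries it out with the same visible procedure in both arms. Either of two procedures would serve:

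- once-daily dosing for every such participant, on progesterone or placebo; or
- twice-daily dosing kept for everyone, with the pharmacy substituting a placebo capsule for one active capsule and the count unchanged.

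Record each use of the rule and any known unblinding, so that both can be reported by arm at the end.

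The cost is one protocol sentence and one pharmacy instruction. The reduced active dose, the sample size and the analysis stay as they are. If the pharmacy already works this way, the change only writes it down.

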Study Design. This double-blind, randomized pilot clinical trial will prescreen an estimated 250 potential subjects, consent and further evaluate approximately 100 potential subjects, and ultimately enroll 70 subjects to ensure 40 subjects will provide a primary marijuana reduction outcome measure at four weeks post quit date. Subjects will be stratified by sex then randomized to one of two treatment groups (n=20 per drug group, 50% female): progesterone (PRO; 200mg 2x/day) or Placebo (PBO). They will take the medication for 5 weeks and will attend weekly clinic visits (see Visit Sequence & Procedure below for more information).

Setting: This project will be conducted at the Delaware Clinical Research Unit (DCRU). The DCRU has both inpatient and outpatient resources for the spectrum of biomedical research including special capabilities that were developed for study of substance use disorders. The Clinical and Translational Sciences Institute (CTSI), runs the DCRU and functions parallel to and supports the activities of the NIH funded CTSI, which it predicated. The DCRU includes: reception area, examination rooms, meeting rooms, clinical interview rooms, testing rooms for computer based performance tasks, a wet lab for handling bloods and other specimens, freezers (to -80°C), all essential staff offices, each with multiple telephone and computer lines through the University of Minnesota servers, locked limited access protocol, equipment and medication rooms, as well as secure cabinets for study files and essential supply and support areas and services.

Recruitment: To meet recruitment goals, we aim to enroll a total of 70 subjects (~6 subjects/month) to ensure a final sample size of 20 females and 20 males completing the study. Our primary recruitment method will be advertising in the mainstream media. While this type of recruitment can be challenging, our team has been successful with this form of recruitment. For example, our current study (PRO for smoking cessation) has had success with Facebook, Craigslist, TV, and radio advertising. Specifically, over the past seven months, we have received an estimated 300 phone calls from interested participants which resulted in the enrollment of 30 subjects (~8 subjects/month).

Study Sample. This study will enroll males (n=35) and females (n=35) who self-report use marijuana ≥4 days per week and are interested in changing their marijuana use. Specific eligibility criteria are as follows:

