Addressing Hypothesis 1a: An unadjusted assessment of the treatment effect will come from a linear model of percent reduction in marijuana use on randomized treatment assignment, separately by sex. **Hypothesis 1b:** A linear model including both males and females will be used to estimate the overall gender effect on percent reduction in marijuana use. **Hypothesis 1c:** A linear model including both males and females will be used to estimate the association of serum progesterone with percent reduction in marijuana use; we will separately consider baseline progesterone, cumulative progesterone (summed over weeks 0-4), and week 4 progesterone.

Addressing Hypothesis 2a: A linear model including both males and females will be used to estimate the association of impulsivity with percent reduction in marijuana use. **Hypothesis 2b:** A linear model including both males and females will be used to estimate the interaction between baseline impulsivity and baseline serum progesterone on percent reduction in marijuana use.

Missing data plan: Quality assurance plans are described below. The primary outcome analysis will be carried out using two parallel models: one model will exclude subjects for whom we were unable to obtain a week 4 TLFB or urine THC. Since 'missing at random' is a strong statistical assumption to make, we will also carry out a parallel model that uses multiple imputation of the week 4 TLFB and urine THC based on an individual's previous visits' TLFB and urine THC levels. We will also examine whether persons missing their week 4 visit differed in their baseline characteristics or treatment assignment from persons not missing their week 4 visit.

Power: This is a pilot study to generate data to potentially motivate and justify a future fully-powered study of PRO and marijuana use. This study will estimate magnitude and direction of treatment effects and associations with impulsivity (sex-specific and overall). Hence, no power calculations are provided.

Data Safety and Monitoring Plan, Board, and Administration.

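### The only planned between-arm comparison for binary adverse events is Fisher's exact test, with no risk difference, interval or upper bound

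*Combined protocol and SAP*

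**What the plan says.** The Adverse Events paragraph under Trial Safety is the only text on how adverse events are analysed. Events are tabulated by sex and arm and then "compared across treatment groups with Fisher's exact test (for binary events) or with chi-square test (for counts of events or event rates"). No effect measure, interval, upper bound, significance level or analysis set is named, and there is no rule for reading a non-significant result.

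The Power paragraph of the Analysis Plan takes a different line for the other outcomes: "This study will estimate magnitude and direction of treatment effects and associations with impulsivity (sex-specific and overall). Hence, no power calculations are provided".

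On numbers, the Study Design paragraph plans to "ultimately enroll 70 subjects to ensure 40 subjects will provide a primary marijuana reduction outcome measure at four weeks post quit date", and describes the two arms as "n=20 per drug group, 50% female". The Study Sample paragraph adds: "This study will enroll males (n=35) and females (n=35"). On expected harms, the Progesterone paragraph under Study Medication states: "The most common adverse effect in males and females is sedation". It lists breakthrough bleeding and breast tenderness for women, and nausea for both sexes, as less common. No rates are given for any of these.

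**The concern.** For marijuana use and impulsivity, the plan sets out to estimate size and direction because the trial claims no power. The same reasoning applies to harms, yet there the stated between-arm method is a significance test. In a trial of this size, a Fisher p-value for an uncommon event says little. It can be well above 0.05 when the true rate on progesterone is twice that on placebo, and it does not show how large an excess the data still allow.

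That excess is the safety figure a larger follow-on trial would need. If the report gives only counts and p-values, a row of non-significant results may be taken as more reassuring than the data justify. This point covers the Fisher test for binary events, not the chi-square test for counts or rates.

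**Working it through.** The plan states no safety sample size, power or event rate, so it has no figure to reproduce.

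**Inputs**
- Arm sizes: 70 enrolled at 1:1 gives 70/2 = 35 per arm at most. The expected completers are 20 per arm. Within one sex, 35 enrolled at 1:1 splits about 18/17, and the completers are 10 per arm.
- Level: two-sided 0.05 (assumed; none is stated).
- Placebo rate: 5% to 30%, doubled or tripled on progesterone (assumed; none is given).

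**Miss rate of the planned test.** With n and m participants on progesterone and placebo and true rates p and q,

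miss rate = 1 - Σ Bin(a; n, p) × Bin(b; m, q),

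summed over all count pairs (a, b) with Fisher p ≤ 0.05. Exact enumeration gives, in percent:

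| Placebo vs progesterone | 35/35 | 20/20 | 18/17 (one sex) | 10/10 (one sex) |
|---|---|---|---|---|
| 5% vs 10% | 97.0 | 98.3 | 98.6 | 99.9 |
| 10% vs 20% | 87.1 | 92.8 | 93.3 | 98.8 |
| 20% vs 40% | 64.3 | 80.8 | 82.2 | 94.2 |
| 30% vs 60% | 37.7 | 65.3 | 60.5 | 87.7 |
| 5% vs 15% | 86.4 | 93.0 | 94.5 | 99.4 |
| 10% vs 30% | 54.5 | 75.8 | 78.0 | 94.3 |
| 15% vs 45% | 27.3 | 55.7 | 59.8 | 85.9 |
| 20% vs 60% | 9.0 | 35.0 | 35.6 | 74.7 |

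**Placebo rate at which the miss rate is 50%.** Below these rates the test misses more often than it detects.

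| | 35/35 | 20/20 | 18/17 | 10/10 |
|---|---|---|---|---|
| Doubling | 25% | 36% | 34% | 48% |
| Tripling | 11% | 16% | 17% | 27% |

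**Smallest significant count.** With no events on placebo, 5/35 on progesterone gives p = 0.054 and 6/35 gives p = 0.025. At 20 per arm, 5/20 gives p = 0.047.

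**What an interval adds.** Take 7/35 on progesterone and 3/35 on placebo. Fisher p = 0.31. The risk difference is d = 0.200 - 0.086 = 0.114. The Wilson 95% limits are 0.100 to 0.359 for 7/35 and 0.030 to 0.224 for 3/35. Newcombe's limits are then:
- lower: 0.114 - √[(0.200 - 0.100)² + (0.224 - 0.086)²] = -0.056
- upper: 0.114 + √[(0.359 - 0.200)² + (0.086 - 0.030)²] = 0.283

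The data are compatible with anything from 6 points fewer to 28 points more on progesterone. A tripled count, 9/35 versus 3/35, gives p = 0.11 with an interval of -0.9 to +34.4 points.

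**Events not seen.** The exact two-sided 95% upper limit for 0/n is 1 - 0.025^(1/n): 10.0% for n = 35, 16.8% for n = 20 and 30.8% for n = 10.

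**The case against.** The strongest reply is that little is lost. The same sentence that names Fisher's test also has events quantified by sex and arm, so any reader with the counts and arm sizes can derive a risk difference and its interval. Events are also graded for relatedness and reviewed by the monitoring board. Low power for harms is common to every pilot of this size, this one openly disclaims power, and no decision in the plan turns on these tests. Nor does the efficacy text promise confidence intervals.

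Much of this is right, and it rules out three stronger readings that a reader might infer.
- That the p-value is all anyone will have to judge harm by. By-arm counts are planned, so this is not so.
- That any doubled or tripled rate would usually go undetected. This depends on a placebo rate the documents do not give. At 35 per arm, tripling from 15% or 20% is missed only 27% or 9% of the time. Sedation, named as the commonest effect, is the weakest example, because higher rates give the test more power.
- That the plan treats p above 0.05 as proof of safety. No level, margin or such rule is stated.

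What remains is narrower. Counts by arm are not a planned estimate of the difference with its precision, and neither relatedness grading nor board review supplies one. Intervals will not create power, but they show how little the data exclude.

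**Conclusion.** The point holds as a gap in the planned safety reporting. For binary adverse events, the stated between-arm method is a test that gives no size of difference and no precision, in a pilot that otherwise aims at estimation. The size of the problem depends on the true placebo rate. Under the assumed two-sided 0.05 level, most doublings are missed when that rate is below about 25% at 35 per arm or 36% at 20 per arm. For triplings the limits are about 11% and 16%. A non-significant result is therefore weak evidence about less common effects, and weaker still within one sex, which is the relevant group for breakthrough bleeding. For a common effect that triples, the test at 35 per arm performs well. The change is worth making because it is cheap; nothing here invalidates the trial.

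**What to change.** Revise the Adverse Events paragraph under Trial Safety as follows.
- For each binary event, and for any adverse event, report the number and percentage of participants by arm, and the progesterone-minus-placebo risk difference with a 95% score or Newcombe interval.
- Give this by sex and overall, with the overall estimate stratified by sex, and for women only for breakthrough bleeding.
- For an event not seen in an arm, report the exact upper 95% limit and say whether it is one- or two-sided.
- Keep Fisher p-values as descriptive only, and state that a non-significant one will not be read as similar safety.

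The cost is a few sentences and some extra table columns, with no new data, visits or participants. The intervals will be wide, so the safety statement will look less reassuring.
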